All subjects will be tested for the presence of the Hepatitis B Virus (HBV) at Screening. A positive result for the Hepatitis B surface antigen (HBs Ag) will be exclusionary. Samples that are negative for HBs Ag will be tested for surface antibodies (HBs Ab) and core antibodies HBc Ab Total). Subjects with HBs Ag (-), HBs Ab (-), and HBc Ab Total (+) require PCR qualitative testing for HBV DNA. Any HBV DNA PCR result that meets or exceeds detection sensitivity will be exclusionary.

Subjects with a negative HBs Ag test and tests showing the results below, do not require HBV DNA PCR qualitative testing.

- HBc Ab Total (-) and HBs Ab (-)
- HBc Ab Total (-) and HBs Ab (+)
- HBc Ab Total (+) and HBs Ab (+)

Hepatitis C Testing:

Blood samples for Hepatitis C serology will be obtained at the Screening Visit. A subject will not be eligible for study participation if test results indicate active Hepatitis C (HCV RNA detectable in any subject with anti HCV Ab).

Pregnancy Test

A serum pregnancy test will be performed at the Screening Visit on all female subjects of childbearing potential. At the Baseline Visit, subjects of childbearing potential will have a urine pregnancy test performed locally by designated study personnel. A serum

pregnancy test will also be taken on Day 1 if the urine pregnancy test is positive. If the serum result at Day 1 is positive, the subject is considered a screen failure. Investigators may conduct more frequent urine pregnancy testing as necessary according to their judgment. If any urine pregnancy test is positive, a serum pregnancy test will be performed by the central laboratory. A lactating or pregnant female will not be eligible for participation or continuation in this study.

Starting at baseline, all women of childbearing potential will have a urine pregnancy test performed locally by designated study personnel at each visit, including at the last dose and PD visit, if applicable (see [Appendix C](#)).

Clinical Laboratory Tests

Blood and urine samples will be obtained for clinical laboratory tests. Samples will be obtained at the designated study visits as specified in [Appendix C](#). Samples will be obtained for the laboratory tests listed in [Table 1](#).

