6.1.1 Definitions

6.1.1.1 Adverse Event

An adverse event (AE) is defined as any untoward medical occurrence in a patient or clinical investigation subject administered a pharmaceutical product and which does not necessarily have a causal relationship with this treatment. An adverse event can therefore be any unfavorable and unintended sign (including an abnormal laboratory finding), symptom, or disease temporally associated with the use of a medicinal (investigational) product, whether or not the event is considered causally related to the use of the product.

Such an event can result from use of the drug as stipulated in the protocol or labeling, as well as from accidental or intentional overdose, drug abuse, or drug withdrawal. Any worsening of a pre-existing condition or illness is considered an adverse event.

Worsening in severity of a reported adverse event should be reported as a new adverse event. Laboratory abnormalities and changes in vital signs are considered to be adverse events only if they result in discontinuation from the study, necessitate therapeutic medical intervention, [meets protocol specific criteria (see Section 6.1.7 regarding toxicity management)] and/or if the investigator considers them to be adverse events.

An elective surgery/procedure scheduled to occur during a study will not be considered an adverse event if the surgery/procedure is being performed for a pre-existing condition and the surgery/procedure has been pre planned prior to study entry. However, if the pre-existing condition deteriorates unexpectedly during the study (e.g., surgery performed earlier than planned), then the deterioration of the condition for which the elective surgery/procedure is being done will be considered an adverse event.

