7.2.1.6 Adverse Events of Special Interest

The Adverse Events of Special Interest (AESI) categories by SOC and PT will be summarized and presented by the two treatment groups in Part 1 and by the four treatment groups in Part 2. The details of AESI list and search criteria are stated in Appendix A, which are extracted from Adalimumab Product Safety Statistical Analysis Plan Version 8.0.

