9.0 Appendix

Appendix A. AESI List and Search Strategies

There are two types of search strategies may be used for categorizing AESI categories are as follow:

- Lowest Level MedDRA Queries (LMQs).
- Standard MedDRA Queries (SMQs)/Company MedDRA Queries (CMQs)/Product-specific MedDRA Queries (PMQs)

LMQs will be the default search strategy unless otherwise stated in the safety analysis request. SMQs/CMQs/PMQs will have limited use as a search strategy, e.g., aggregated safety review or any other special requests as deemed appropriate. LMQs will be used in our study.

The following table includes all AESI for Humira with the LMQ searches.

AESI	LMQ Name	LMQ Search Term Definition
Infection		
All Infection	Infection LMQ	Terms clearly identifying an infection.
Serious Infection	Infection LMQ	All Infections – Subset for SAEs.
Legionella Infection	Legionella Infection LMQ	Terms Legionella infections. Culture and isolation of Legionella from respiratory secretions and/or pleural fluid. Direct fluorescent antibody (DFA) staining that identifies Legionella in respiratory secretions and/or pleural fluid. Four-fold increase in Legionella antibody titer or a single titer of 1:128.
Diverticulitis	Diverticulitis LMQ	Leukocytosis, CT Findings (Phlegmon, free air bubbles, abscess, colonic wall thickening, free fluid, obstruction), Fistulas (colovesica, rectovaginal).

AESI	LMQ Name	LMQ Search Term Definition
Infection (continued)		
Opportunistic Infection Excluding Oral Candidiasis and TB	Opportunistic Infection LMQ	Terms describing unusually severe forms of infections by a microbe typically seen only in immunocompromised individuals e.g., the term 'Herpes sepsis' is included. Investigations for infections that generally occur exclusively in immunocompromised patients e.g., JC virus test positive. Broader terms for infections typically only seen in immunocompromised persons when a more specific term for that infection type is not available e.g., the term 'stomatoccal infection' is included. Terms describing specific forms of fungal infections or tuberculosis infections which typically occur only in immunocompromised patients e.g., the term 'disseminated TB' is included.
Oral Candidiasis	Oral Candidiasis LMQ	Terms describing Oral Candidiasis only.
Tuberculosis		Active tuberculosis and latent tuberculosis combined.
Active Tuberculosis	Active Tuberculosis LMQ	Terms that describe active disease of tuberculosis.

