Latent Tuberculosis	Latent Tuberculosis LMQ	Terms that describe positive results for TB screening tests (either skin or blood tests). Terms that describe TB infection or latent infection.
Parasitic Infection	Parasitic Infection LMQ	Protozoal infectious disorders, Helminthic Disorders, and Ectoparasitic infestations. Skin and subcutaneous arthropod and parasitic infestations, Parasitic lower respiratory tract infections. Investigations terms for parasite identification and serology tests.
Reactivation of Hepatitis B	Reactivation of Hepatitis B Viral Infection LMQ	HBVsAg positive, HBeAb positive, PCR test for viral titer, HBVsAb positive, HBVc Ab positive.
Progressive Multifocal Leukoencephalopathy (PML)	Progressive Multifocal Leukoencephalopathy LMQ	PML definitive diagnosis.

AESI	LMQ Name	LMQ Search Term Definition
Malignancies		
Malignancies	Malignancies LMQ	
All MedDRA terms for malignant or unspecified tumors:
 
 • Malignancy related conditions. • Terms for malignancy related conditions. • Terms for therapeutic and diagnostic procedures used to treat malignancies; treated malignancy to be specified. • Some of these procedures are also used for the treatment of non-malignant conditions. • Laboratory tests (incl. the results) that are specific for the malignancies. • To make agreement on "in situ" stage whether they fall under malignancies or not; currently assessed as malignancies. • To make agreement on general terms of "neoplasm;" whether considered as malignancies when no further details provided. • Tumour markers. • Terms related to tumor markers including the result. 
For European Group on Tumour Markers, please reference the web site at http://ar.iiarjournals.org/content/27/4A/1901.abstract:
 
 • Terms related to benign tumors. • Terms related to premalignant conditions. • Treatment and diagnostic procedures that do not specify a malignancy indicated. • Malignancy related therapeutic and diagnostic procedures includes a variety of terms which describe chemotherapy or radiotherapy treatment. 
Please be aware, however, that there are some terms which relate to chemotherapeutic. Such terms are not linked to chemotherapy or radiotherapy terms.

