Lupus-Like Reactions and Systemic Lupus Erythematosus (SLE)	Lupus-Like Reactions and Systemic Lupus Erythematosus (SLE) LMQ	Lupus erythematosus and associated conditions in both primary and secondary locations in this are included except Lupoid hepatic cirrhosis, which is excluded. Additional terms representing the diagnostic criteria of the American College of Rheumatology (ACR), e.g., Malar rash, Arthritis, Renal disorder, etc.

AESI	LMQ Name	LMQ Search Term Definition
Immune Reactions (continued)		
Vasculitis	Vasculitis LMQ	
Terms for primary vasculitides (e.g., Henoch-Schonlein purpura, Behçet's syndrome, or Granulomatosis with polyangiitis (which includes Wegener's granulomatosis).
 
Terms containing vasculitis (e.g., Cutaneous vasculitis, Lupus vasculitis, or Rheumatoid vasculitis).
 
Terms containing arteritis (e.g., Arteritis coronary or Polyarteritis nodosa).
 
Terms containing angiitis (e.g., Microscopic polyangiitis or Thromboangiitis obliterans).
 
Terms for forms of purpura indicative of a vascular condition such as Henoch Schonlein purpura and Chronic pigmented purpura (narrow, which includes Majocchi's purpura) and Palpable purpura (broad).
 
Terms for laboratory test results that may indicate vasculitis (e.g., Antineutrophil cytoplasmic antibody increased).

Cutaneous Vasculitis	Cutaneous Vasculitis LMQ	Terms for vasculitides clearly identifiable as cutaneous (e.g., Cutaneous vasculitis, Skin vasculitis, Majocchi's purpura, Leukocytoclastic vasculitis, vasculitis legs, Necrotizing vasculitis, polyangiitis or Vasculitic rash).
Non-Cutaneous Vasculitis		Terms for vasculitides that are NOT in Cutaneous Vasculitis LMQ.
Sarcoidosis	Sarcoidosis LMQ	Sarcoidosis of any organ.
Autoimmune Hepatitis	Autoimmune Hepatitis LMQ	
Cardiovascular/Vascular		
Myocardial Infarction	Myocardial Infarction LMQ	
Myocardial Infarction.
 
Terms which included the words 'myocardial infarction, heart attack, cardiac enzymes increased, cardiac troponin increased, CK-MB increased, ECG ST elevation, Q wave abnormal.'

Cerebrovascular Accident	Cerebrovascular Accident LMQ	Terms for conditions specific for cerebrovascular accident disorders irrespective of cause and irrespective of acuteness or chronicity.

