Worsening and New Onset of Psoriasis	Worsening New Onset of Psoriasis LMQ	Psoriasis can present in guttate form, where the lesions are smaller, or involve flexural parts of the body (e.g., axilla, inframammary areas), or involve fingernails or toenails (i.e., nail psoriasis), or involve palms or soles. In pustular psoriasis, the presentation is characterized by sterile pustules on a brightly erythematous base. When pustular psoriasis involves the palms and soles, it is termed palmoplantar pustulosis. Other variants of psoriasis include psoriasiform dermatitis and acrodermatitis continua.

AESI	LMQ Name	LMQ Search Term Definition
Nervous System Disorder		
Demyelinating Disorders Including Multiple Sclerosis, Guillain-Barré Syndrome, and Optic Neuritis and Others	Demyelinating Disorders LMQ	Terms for encephalomyelitis and leukoencephalopathies related to demyelination (e.g., Acute haemorrhagic leukoencephalitis and Progressive multifocal leukoencephalopathy). Trigeminal neuralgia is included in broad terms due to possible association with multiple sclerosis or other demyelinating conditions. Terms representing a disability scale which is highly specific for MS (e.g., Expanded disability status scale score increased).
Amyotrophic Lateral Sclerosis	Amyotrophic Lateral Sclerosis LMQ	There are no specific tests to provide a definite diagnosis of ALS although the presence of upper and lower motor neuron signs in a single limb is strongly suggestive. The diagnosis is based on symptoms and signs as well as a series of tests to assess muscle weakness and atrophy, hyperreflexia, and spasticity which gets progressively worse. For these reasons the search terms recommended for adjudication purposes would need to be consistent with the diagnosis of ALS and not with non-specific findings describing all the different types of motor neuron diseases. Patients may exhibit symptoms and signs of the disease such as hyperreflexia, and spasticity. Tests such as muscle biopsy, nerve conduction velocity, electromyography as well as MRI scans of the brain or spinal cord may also point to a possible diagnosis of ALS although none of these tests are definitive and will therefore not be included in the search.
Amyotrophic Lateral Sclerosis (continued)		ALS-related syndromes include progressive muscular atrophy, primary lateral sclerosis and progressive bulbar palsy will be included in the search.

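### The AESI searches are not fitted to psoriatic arthritis: the lupus-like and psoriasis category totals can mix disease flares with drug reactions

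*SAP*

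**What the plan says.** SAP 7.2.1.6 plans a summary of AESI categories by system organ class and preferred term, for the two groups in Part 1 and the four groups in Part 2. It says the list and search criteria are "extracted from Adalimumab Product Safety Statistical Analysis Plan Version 8.0". Appendix A confirms the search type: "LMQs will be used in our study".

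Two categories matter here.

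- **Lupus-like reactions and SLE.** Besides lupus and associated conditions, the search takes in "Additional terms representing the diagnostic criteria of the American College of Rheumatology (ACR), e.g., Malar rash, Arthritis, Renal disorder, etc".
- **Psoriasis.** The category is "Worsening and New Onset of Psoriasis", served by a single search, the "Worsening New Onset of Psoriasis LMQ". Its definition also covers pustular and palmoplantar forms.

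Protocol 6.1.1.1 defines what can enter these rows: "Any worsening of a pre-existing condition or illness is considered an adverse event". It makes no exception for psoriatic arthritis or psoriasis. Inclusion criterion 4 requires at least 3 tender and 3 swollen joints at screening and baseline.

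**The concern.** A product-level search is built to work across indications. In most of them, arthritis or psoriasis appearing on treatment is unexpected and may point to a drug reaction. In this trial they are the disease under study. A joint flare recorded under the term *Arthritis* would be counted in the lupus-like category, and a skin flare would be counted together with psoriasis arising for the first time on treatment.

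The rows exist to show reactions that the protocol itself associates with adalimumab: its benefit-risk section (3.4) lists lupus and lupus-related conditions among reported reactions. If flares are reported at different rates in the arms, the category totals carry that difference as well as any drug effect. The trial is open-label, so blinding gives no protection against differential reporting.

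**Working it through.** **1. Plan figures.** The plan states no figure for these categories. The only planned number used below is the denominator of 120 per arm (SAP 4.4). It reproduces: 40% vs 20% at two-sided 0.05 and 90% power needs 109 per arm, and 109 × 1.1 = 119.9, or 120 (109 / 0.9 gives 122).

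**2. Was the list fitted to this trial?** Appendix A still carries an intestinal stricture row that its own footnote restricts to the Crohn's disease programme, and neither document states any adaptation for psoriatic arthritis. The appendix does accept the principle of fitting: the stricture row is limited by indication, and the amyotrophic lateral sclerosis row asks for terms consistent with the diagnosis and leaves out non-specific findings.

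**3. How mixing could act in Part 1.** The documents give no rates, so this is an assumed range. Let *r* be a true adalimumab excess of the reaction, and *fA* and *fM* the shares of subjects with a flare event caught by the row on adalimumab + MTX and on escalated MTX. With independence, the adalimumab row is 1 − (1 − r)(1 − fA) and the MTX row is fM. Example: r = 2%, fA = 2.5% gives 1 − 0.98 × 0.975 = 4.45%.

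| r | fA 0, fM 0 | fA 1%, fM 2% | fA 2.5%, fM 5% | fA 5%, fM 10% |
|---|---|---|---|---|
| 1% | 1.00% vs 0 | 1.99% vs 2% | 3.475% vs 5% | 5.95% vs 10% |
| 2% | 2.00% vs 0 | 2.98% vs 2% | 4.45% vs 5% | 6.90% vs 10% |
| 3% | 3.00% vs 0 | 3.97% vs 2% | 5.425% vs 5% | 7.85% vs 10% |

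At 120 per arm, an excess of 1%, 2% or 3% is 1.2, 2.4 or 3.6 subjects. The category total shows an adalimumab excess only if r(1 − fA) > fM − fA. That threshold is r > 0.01/0.99 = 1.0% in the third column, 0.025/0.975 = 2.6% in the fourth and 0.05/0.95 = 5.3% in the fifth. If few flares are reported, or they are reported equally in both arms, the direction of an excess survives. The halving of the flare rate on adalimumab is assumed.

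**4. Part 2.** Arms 1 and 3 contain Week 16 MDA achievers; Arms 2 and 4 contain non-achievers. Arm 3 is the only arm without adalimumab, so it compares MTX-alone achievers with adalimumab arms that include all the non-achievers. Flare terms could then add to the adalimumab rows. Equally, achievers can lose control, including those in Arm 1 whose MTX is withdrawn. The direction cannot be fixed in advance.

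**5. What the planned output separates.** For lupus, display by preferred term puts *Arthritis* and a lupus term on separate lines. For psoriasis, a preferred term need not say whether the subject had psoriasis before. True new onset is possible: CASPAR can be met on personal or family history without current psoriasis (Protocol 5.3.1.1). No planned table or listing makes this split.

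**The case against.** The strongest reply is that the plan already lets a reader see through the lupus total. AESIs are shown by preferred term, so a single lupus case on adalimumab has its own line. Diagnosed lupus-like syndrome is a withdrawal criterion (Protocol 5.4.1), and events leading to discontinuation of study drug are listed and tabulated (SAP 7.2.2). This stands: for lupus, mixing affects the category total and little else. It does not help with psoriasis.

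Second, Appendix A gives summary definitions and no term lists. Protocol 6.1 asks for the event diagnosis where known, so a flare may be recorded as psoriatic arthritis, and whether the lupus search catches that term is unknown. This also stands, and it is why no size can be claimed.

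Third, worsening of psoriasis is named in the category and is itself monitored, so it should not be dismissed as mere lack of efficacy. That is right, and it is a reason to show the two components separately, not to remove one.

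Fourth, SAP 7.2.1.1 permits extra adverse event tabulations on recommendation from Clinical and Safety. It permits them but does not specify these.

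**Conclusion.** The point holds in a limited form. Following the SAP as written, the lupus-like and psoriasis category totals can combine disease activity with drug reactions. The psoriasis pooling is the firmer half. The effect is on descriptive safety reading only: no test is planned on AESI rows, and the primary result is untouched. The size is unknown, and the dilution shown for Part 1 depends on flares being reported less often on adalimumab, which is plausible but assumed.

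Three stronger readings are tempting, and the documents do not support them.

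- *The rows measure disease control instead of drug reactions.* The text shows possible mixing; the share cannot be known without the term lists.
- *The planned response rates give the size or direction.* Rates of 40% and 20% leave 120 × 0.60 = 72 and 120 × 0.80 = 96 subjects out of MDA. But every subject is out of MDA at screening (inclusion criterion 3), so remaining there is not worsening and does not by itself produce an adverse event.
- *The hepatitis B reactivation row, defined by "HBVsAg positive, HBeAb positive, PCR test for viral titer, HBVsAb positive, HBVc Ab positive", counts antibody status at entry.* Appendix C of the protocol schedules serology only at screening, and AESIs sit within the treatment-emergent section, which requires onset on or after first dose. Entry status should therefore not feed that row.

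**What to change.** In SAP 7.2.1.6 and Appendix A:

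1. Keep both product-level rows unchanged, for comparability with other adalimumab studies.
2. Add a lupus line restricted to lupus and lupus-like diagnoses, leaving out *Arthritis* as a stand-alone term.
3. Split the psoriasis row into (a) worsening of psoriasis present at baseline and (b) new-onset or new-form (pustular, palmoplantar) psoriasis. Define baseline status from the psoriasis history and the PASI and BSA collected at screening and baseline, and state where a recurrence counts when a subject has a history but clear skin at baseline.

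No new data are needed. The cost is SAP wording and minor programming. The drawback is that the added lines will differ from the product-level search, so they should be labelled as study-specific.
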